4. HYPOTHESES AND DECISION RULES

Because of the non-confirmatory nature of this study, no hypothesis tests will be performed in this study.

4.1. Statistical Hypotheses

No hypothesis tests will be performed.

4.2. Statistical Decision Rules

Not applicable.

5. ANALYSIS SETS

5.1. Safety Analysis Set

The safety analysis set is the full analysis set that is as close to all subjects who have given consent to participate in this study as possible. Specifically, the safety analysis set consists of all subjects who gave consent to participate in this study except those who meet at least one or more following conditions:

1. No case report form is collected. (Indicated as “CRF not collected” in the study report.)
2. Any violation or deficiency is found concerning the study contract. (Indicated as “Contract violation/deficiency” in the study report.)
3. The registration does not meet all the requirements. (Indicated as “Invalid registration” in the study report.)
4. No information is reported for adverse events. – No report after participation in this study (Indicated as “No AE information” in the study report.)

Details of each criterion follow the Guidance for Adoption/Rejection Criteria for Analysis Populations and Handling of Data in Drug Use-Results Surveys.

5.2. Effectiveness Analysis Set

Not applicable.

5.3. Other Analysis Sets

Not applicable.

5.4. Subgroups

Subgroup analyses of safety will be performed with respect to the following recipient characteristics (factors). The subgroups in each categorization are indicated in the squared brackets [] with the reference for risk ratio/difference being underlined.

- Sex [male, female]

- Age [<55 yrs., ≥55 yrs.], [<65 yrs., ≥65 yrs.]
- Past history of allergy [absent, present]

In addition, subgroup analyses of safety with respect to other factors indicated below will be performed, as necessary:

- Suspected pregnancy/Lactation (women only, for each dose number for initial immunization) [absent, present]
- Pregnancy (women only) [absent, present]
- Lactation (women only) [absent, present]
- History of other vaccination (except boosts) [absent, present]
- Renal impairment [absent, present]
- Hepatic impairment [absent, present]

Presence/absence of renal/hepatic impairment should be determined according to “Attachment: Procedure to Extract Patients with Hepatic/Renal Impairment in Post-Marketing Investigations”.

6. ENDPOINTS AND COVARIATES

6.1. Safety Endpoints

- Serious adverse events or serious adverse reactions: Adverse events/reactions considered by the physician to be serious

Events in the scope of the safety specification will be specified separately.

6.2. Efficacy Endpoints

Not applicable.

6.3. Other Endpoints

Not applicable.

6.4. Covariates

No covariates or potential covariates have been identified for the safety or effectiveness of this product on the basis of currently available data including those from clinical studies.

7. HANDLING OF MISSING DATA

If the action taken for an AE or outcome of an AE is missing, they will be treated as having a value of “unknown” for data tabulation. If the causality of an AE is missing, the event will be treated as “causally related” for data tabulation.

Cleaning-uncompleted data will be in principle handled as follows:

- Items for which relevant data are missing: For both tabulation and listing, their values will be handled as missing data (or they will be treated as “unknown” for a categorical variable).
- Items for which relevant data are inconsistent: For both tabulation and listing, their values will be handled as missing data. In addition, a list will be presented separately for details of data-handling.
- Items with no signature: For both tabulation and listing, any record in a CRF with no signature of a contract physician (including when the CRF is signed only by individuals other than contract physicians) will be handled as missing data. A record in the CRF will be regarded as having no signature if the date is missing despite presence of a space for date or an inconsistent date (e.g., a future date) is filled in.

8. HANDLING OF DATA WITH MISSING INFORMATION ON BOOSTER (THIRD) VACCINATION

If for a subject it cannot be determined whether booster (third) vaccination was given or not or although booster vaccination was confirmed to have been given but its date is unknown, the subject's data covered by CRF Booklet 02 (i.e., data from the day following 6 months after the final vaccination with this product for the initial immunization to 12 months [52 weeks] following the final vaccination with this product for the initial immunization) will be excluded from the safety analysis. Data excluded should be those from the next day of completion (termination) of observation (final observation day) for CRF Booklet 01 (or for data lacking information of date, data collected in CRF Booklet 02 should be excluded), and a separate list of excluded data will be prepared.

9. STATISTICAL METHODS AND ANALYSES

Copied data from the Investigation of Health Status of Recipients Vaccinated First that have been stored in the database for this study will be appropriately reviewed according to Pfizer's coding rules, as necessary, e.g., when multiple pieces of information are contained in the same field. For tabulations and listings defined in this SAP, data after review will be used; data given the “Out of Scope for Coding” status will not be included in those tabulations or listings.

9.1. Statistical Methods

9.1.1. Continuous variables

For continuous variables, summary statistics (n, mean, standard deviation [SD], median, maximum, minimum) will be presented.

9.1.2. Categorical variables

For categorical variables, subjects included in each category will be calculated in terms of frequency (such as n) and proportion.

9.1.3. Binary variables

For binary variables, subjects included in each binary category will be calculated in terms of frequency and proportion. When a confidence interval (CI) is determined for a proportion, the two-sided 95% CI (exact method) will be determined.

When a comparison for proportion is made between subgroups, the risk ratio and its 95% CI will be calculated. They will also be presented graphically (See Appendix 1).

9.2. Statistical Analyses

9.2.1. Subject description

9.2.1.1. Constitution

Among CRF-collected subjects, those included in the safety analysis set will be tabulated. In addition, subjects excluded from the safety analysis set, and those excluded from the safety analysis set for each reason will be tabulated.

9.2.1.2. Vaccination discontinuation and dropouts

Using the safety analysis set, subjects who discontinued this study will be summarized in terms of n and proportion. Summarization will also be performed by reason of discontinuation for both n and proportion. Reasons for discontinuation are categorized into adverse events, death, lost to follow-up, consent withdrawal, or other.

9.2.1.3. Subjects excluded from analysis

Subjects excluded from the safety analysis set will be listed in tabular form with their reasons for exclusion.

9.2.2. Subject characteristics and treatment history

9.2.2.1. Subject characteristics

Using the safety analysis set, characteristics of vaccinated subjects collected in the Investigation of Health Status of Recipients Vaccinated First will be summarized according to Section 8.1, with respect to the following factors:

- Sex [male, female]
- Age (continuous)

- Age (categorical) [≥ 0 to <10 yrs., ≥ 10 to <20 yrs., ≥ 20 to <30 yrs., ≥ 30 to <40 yrs., ≥ 40 to <50 yrs., ≥ 50 to <60 yrs., ≥ 60 to <70 yrs., ≥ 70 to <80 yrs., ≥ 80 to <90 yrs., ≥ 90 yrs.]
- Past history [absent, present]
- Complications [absent, present]
- Allergy [absent, present]
- Suspected pregnancy/Lactation (women only, for each dose number for initial immunization) [absent, present]
- Pregnancy (women only) [absent, present]
- Lactation (women only) [absent, present]
- Duration of safety assessment (days)
- Number of doses for initial immunization during the study period for the Investigation of Health Status of Recipients Vaccinated First [1 dose, 2 doses]
- Dose interval for initial immunization (recipients of two doses only) (day of 2nd dose – day of 1st dose)
- Booster (third) vaccination [absent, present (this product, other), unknown]

Using the safety analysis set, a breakdown of subjects according to each of the following factors will be presented in terms of n and proportion by system organ class (SOC) and preferred term (PT):

- Past history
- Complications

9.2.3. Safety analyses

The listings will include all relevant events reported in this study.

9.2.3.1. Adverse reactions

9.2.3.1.1. Serious adverse reactions

Serious adverse reactions will be summarized by SOC and PT in terms of n and proportion. Multiple adverse reactions of the same PT occurring in the same vaccine recipient will be counted only once.

9.2.3.1.2. Details of serious adverse reactions

Serious adverse reactions will be summarized in terms of n and proportion by each of the following factors:

- Action taken (additional treatment) [present, absent]
- Outcome [not recovered, recovered with sequelae, improved, resolved/recovered, death, unknown]
- Severity [mild, moderate, severe, life-threatening]
- Batch number

Subjects who experienced multiple adverse reactions with the same PT will be summarized in the manner described below in terms of summarization of n:

- Days to onset: The days to the first onset will be adopted.
- Action taken (additional treatment): If multiple actions were taken for adverse reactions occurring in the same subject with the same PT, only one kind of action will be adopted with “present” being given priority over “absent”.
- Outcome: The outcome for the last reaction will be adopted.
- Severity: If the same subject experienced multiple adverse reactions with the same PT in different severities, the subject will be handled as having experienced an event of one level of severity with “life-threatening”, “severe”, “moderate”, and “mild” being given priority in this order.

9.2.3.1.3. Onset time of serious adverse reactions

Serious adverse reactions will be summarized in terms of n and proportion (denominator = the number of subjects vaccinated) by the time of first onset [from the day after 28 days following the last dose for initial immunization with this product to 3 months after the last dose for initial immunization with this product, from the day after 3 months following the last dose for initial immunization with this product to 6 months after the last dose for initial immunization with this product, from the day after 6 months following the last dose for initial immunization with this product to 12 months after the last dose for initial immunization with this product] and by SOC and PT. For subjects with booster vaccination, only events that occurred by the day before booster dosing will be included.

9.2.3.1.4. Occurrence of serious adverse reactions in subjects excluded from the safety analysis set

Using data from CRF-collected subjects, serious adverse reactions reported during the entire evaluation period in subjects excluded from the safety analysis set will be identified and presented in tabular form. The adverse reactions identified will also be summarized in terms of n by SOC and PT.

9.2.3.2. Adverse events

9.2.3.2.1. Serious adverse events

Serious adverse events will be summarized by SOC and PT in terms of n and proportion. Multiple adverse events of the same PT occurring in the same vaccine recipient will be counted only once.

9.2.3.2.2. Onset time of serious adverse events

Serious adverse events will be summarized in terms of n and proportion (denominator = the number of subjects vaccinated) by the timing of first onset [from the day after 28 days following the last dose for initial immunization with this product to 3 months after the last dose for initial immunization with this product, from the day after 3 months following the last dose for initial immunization with this product to 6 months after the last dose for initial immunization with this product, from the day after 6 months following the last dose for initial immunization with this product to 12 months after the last dose for initial immunization with this product] and by SOC and PT. For subjects with booster vaccination, only events that occurred by the day before booster dosing will be included.

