2.1. Study Design

[Vaccination Recipients Included in this Study]

Subjects must meet all of the following inclusion criteria to be eligible for inclusion in this study:

- Subjects who participated in the Investigation of Health Status of Recipients Vaccinated First and have provided written informed consent to continued participation in this study.

[Exclusion Criteria]

There are no exclusion criteria for this study.

[Safety Evaluation Period]

Subjects in this study will be followed for 11 months from the day following 28 days after the final vaccination of the initial immunization with this product (i.e., the end of the observation period in Investigation of Health Status of Recipients Vaccinated First).

Subjects who discontinued this study will be followed until the day of discontinuation, and those who received booster vaccination (regardless of whether it is with this product or not) will be followed until the day before the booster vaccination.

[Planned Study Period]

The planned period covered by this study is as follows.

- Investigation period: From the day following the day of completion of the observation period for the first subject who has completed the observation period in the Investigation of Health Status of Recipients Vaccinated First to the end of the observation period for the last subject investigated in this study (scheduled from March 2021 to August 2022)

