2.2. Study Objective

In this investigation, the healthcare professionals who are vaccinated with this product early after the marketing approval of this product (participants in the Investigation of Health Status of Recipients Vaccinated First conducted by the Science Research Group of the Ministry of Health, Labour and Welfare) will be followed for 11 months from the day following 28 days after the final vaccination of the initial immunization with this product (end date of observation period in Investigation of Health Status of Recipients Vaccinated First) to 12 months after the final vaccination of the initial immunization with this product, information on serious adverse events and COVID19 observed during the follow-up period will be collected.

If booster vaccination isn't conducted, the long-term safety after the initial immunization of this product during the follow-up period will be assessed.

In booster vaccination is conducted, the long-term safety after the initial immunization of this product up to the day before booster vaccination will be confirmed, and information on serious adverse events and COVID-19 will continuously obtained after booster vaccination.

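### The onset-window tables keep one fixed denominator and show no observation time per window, so the 6–12 month proportion understates full-window risk in expectation and cannot be compared with earlier windows

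*SAP*

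**What the plan says.** SAP 9.2.3.2.2 summarises serious adverse events as "n and proportion (denominator = the number of subjects vaccinated) by the timing of first onset". SAP 9.2.3.1.3 uses the same measure for serious adverse reactions: "n and proportion (denominator = the number of subjects vaccinated) by the time of first onset". Both use three windows counted from the last initial dose: after day 28 to month 3, months 3 to 6, and months 6 to 12.

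For boosted subjects, "only events that occurred by the day before booster dosing will be included". This matches the safety evaluation period in SAP 2.1, where boosted subjects "will be followed until the day before the booster vaccination" and, for the others who leave early, "Subjects who discontinued this study will be followed until the day of discontinuation".

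When booster status or date cannot be established, SAP Section 8 says that the subject's Booklet 02 data "will be excluded from the safety analysis". The cut is placed as follows: "Data excluded should be those from the next day of completion (termination) of observation (final observation day) for CRF Booklet 01". Booklet 02 covers months 6 to 12 (Protocol 8.2.6).

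No section takes boosted, discontinued or Section 8 subjects out of a window's denominator. None plans a number at risk, person-time or rate by window. The related summaries are overall ones: duration of safety assessment and booster status (SAP 9.2.2.1) and discontinuations by reason (SAP 9.2.1.2).

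**The concern.** The study's purpose is long-term safety after the initial immunization, and months 6–12 are its longest-term part. The two onset tables are the only planned summaries of serious events or reactions by time since vaccination, and the final analysis supports re-examination (SAP Section 3). A reader will naturally look across the three columns for a rise or fall.

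Two things other than risk shape that pattern. Unequal window length raises the last column. Observation lost to boosters, discontinuation or the Section 8 cut lowers it, because the subject stays in the denominator while later events are not counted. Length can be read from the window bounds, but lost observation cannot be read from the table at all. A flat, rising or falling pattern could therefore each arise under a constant event rate.

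**Working it through.** The plan states no expected incidence, event count or precision, so there is no figure of its own to reproduce. The check looks at what the planned proportion would show under a constant event rate.

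**Inputs from the documents.** Window bounds in months (SAP 9.2.3.1.3, 9.2.3.2.2); 6 months = 24 weeks and 12 months = 52 weeks (Protocol 8.2.6); at most 20,000 subjects (Protocol 8.5.1).

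**Assumptions.** Booster uptake p of 10–90%, with all boosters at month m = 7, 8, 9 or 10; no losses before month 6; month 3 = 12 or 13 weeks; 1 month = 4.348 weeks; rare events at a constant rate.

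**1. Window length.**

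| Definition | Weeks per window | Last/first | Last/second |
|---|---|---|---|
| Month 3 = 13 weeks, then weeks 24 and 52 | 9, 11, 28 | 3.1 | 2.5 |
| Month 3 = 12 weeks, then weeks 24 and 52 | 8, 12, 28 | 3.5 | 2.3 |
| Calendar months | 9, 13, 26 | 2.9 | 2.0 |

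With complete follow-up and a constant rate, the 6–12 month proportion is thus 2.0–2.5 times the 3–6 month one.

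**2. Lost observation.** Planned late proportion as a share of full-window risk = 1 − p × (52 − 4.348m)/28.

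| Boosted | Month 7 | Month 8 | Month 9 | Month 10 |
|---|---|---|---|---|
| 10% | 92% | 94% | 95% | 97% |
| 30% | 77% | 82% | 86% | 91% |
| 50% | 62% | 69% | 77% | 85% |
| 70% | 46% | 57% | 68% | 79% |
| 90% | 31% | 45% | 59% | 73% |

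For example, 70% at month 8 gives 1 − 0.7 × 17.216/28 = 0.570. On calendar months the share is 1 − p × (12 − m)/6, and the range is 25–97%.

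**3. Both effects together.** With windows of 9, 11 and 28 weeks, the late/second ratio is 2.55 × share: 2.55 with no boosting, 1.45 for 70% at month 8, 0.78 for 90% at month 7. It drops below 1 when the share is under 11/28 = 0.393, which happens in 1 of the 20 scenarios. On calendar months the threshold is 3/6 = 0.5, and 3 of 20 fall below it: 70% at month 7 (0.417), 90% at month 7 (0.25) and 90% at month 8 (0.40).

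**4. Section 8.** If a fraction s of subjects is cut off exactly at month 6, the late share is multiplied by 1 − s. Fractions of 1, 5 and 10% give factors of 0.99, 0.95 and 0.90. These are maximum losses, because the Booklet 01 final observation day may fall after month 6 (Protocol 8.3.3).

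**5. Illustration.** Take 20,000 subjects and an assumed 0.5 first events per 1,000 person-months. Full late person-time is 20,000 × 28/4.348 = 128,795 person-months.

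| Scenario | Late events / person-months | Planned proportion | Rate per 1,000 person-months (exact 95% CI) |
|---|---|---|---|
| No boosting | 64 / 128,795 | 0.32% | 0.50 (0.38–0.63) |
| 10% at month 10 | 62 / 124,876 | 0.31% | 0.50 (0.38–0.64) |
| 70% at month 8 | 37 / 73,362 | 0.185% | 0.50 (0.36–0.70) |
| 90% at month 7 | 20 / 39,523 | 0.10% | 0.51 (0.31–0.78) |

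The stable rate is built into the assumptions (constant hazard, booster timing unrelated to risk). What the table shows is how far the proportion moves when risk does not.

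**6. Recovery from the duration summary.** Observation runs 20 weeks from week 4 to week 24 and 28 weeks after that, so the late share is roughly (mean duration − 20)/28. For 70% at month 8 the mean is 35.95 weeks, which returns 0.57 correctly. If instead 5% leave at week 10 and nobody is boosted, the mean is 0.95 × 48 + 0.05 × 6 = 45.9 weeks, which returns 0.925 against a true 0.95. The back-calculation fails once losses occur before month 6. The SAP also does not say whether duration is cut for Section 8 subjects.

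**The case against.** The study is descriptive, with no hypothesis tests or decision rules (SAP Section 4), and nowhere does the SAP say that the windows will be compared or that the last column is a 6–12 month risk. The measure is of the same kind as in Protocol 8.7.2: affected subjects over subjects analysed. Counting only pre-booster events is deliberate and follows the objective that "the long-term safety after the initial immunization of this product up to the day before booster vaccination will be confirmed". Duration, booster status, discontinuations, post-booster events and the excluded data are all tabulated or listed, and exploratory analyses are allowed. Rates added now would be post hoc and would rest on booster timing being unrelated to event risk. A footnote might be enough.

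Much of this stands. The planned proportion is valid as defined, the numerator rule should stay, and the window bounds are visible. What does not stand is that exposure is already covered: none of those summaries is by window, and an optional exploratory analysis is not a planned one. A footnote alone would warn the reader but would leave the study without an interpretable late-window figure.

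Three stronger readings are tempting, and the documents do not support them:

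- *Any early exit lowers the figure.* A subject boosted after a first event loses nothing in an any-event row, and adverse events and death are themselves discontinuation reasons. Truncation cannot raise the proportion and lowers it in expectation; no more can be said.
- *The late column will look lower than the earlier ones, or hide a real increase.* Length pushes the other way. The late share falls below one half, the level needed to mask a doubled late rate fully, in only 3 of the 20 assumed scenarios.
- *Section 8 subjects must exist.* An unknown category for booster status was added in SAP 5.0, when all data were fixed. That suggests such subjects but does not prove it.

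**Conclusion.** The point holds as a gap in presentation that is worth fixing, not as an invalid analysis. That the late proportion cannot exceed the value under full observation, and is lower in expectation, follows from the rules themselves and needs no assumed rates. Non-comparability follows from the unequal windows together with unseen losses. Boosting or discontinuation before month 6 would lower the earlier windows too.

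The size is unknown. The percentages above come from an unweighted grid of assumed uptake and timing, not from forecasts, and with low uptake or late boosting the effect is small. Counts of scenarios depend on whether months are read as weeks 24 and 52 or as calendar months, since the onset sections give months only.

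**What to change.** In SAP 9.2.3.1.3 and 9.2.3.2.2 keep n and the stated proportion. For each window add, at minimum for an any-event row:

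- the number at risk at the start of the window;
- the person-time observed in it;
- the first-event rate per 1,000 person-months with an exact Poisson 95% CI.

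Stop person-time at the earliest of first event, day before booster, discontinuation, Section 8 cut-off or month 12. The Section 8 cut-off is the Booklet 01 final observation day. Where that day falls somewhat after month 6, the time up to it stays in the late window together with its data. Put first events without an onset date in a separate row, outside the rates. Do not restore the excluded Booklet 02 data, which could mix in post-booster time.

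Add a footnote that the proportions are not comparable across windows and that the rates assume booster timing is unrelated to event risk, so they are biased too if, for example, illness delays boosting.

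The cost is SAP wording and a few columns. The dates needed are already collected: final observation (Protocol 8.3.3), booster (8.3.4) and event onset (8.3.7). SAP 6.0 carries the status that all data are fixed, so the columns must be labelled as added after data fix. The serious adverse event onset table was itself added at that status, in SAP 5.0. The downside is that late-window figures become less precise.
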